### Overview of Study Protocol (RQ-2)

This project will employ both qualitative and quantitative methods, based on theoretical models adopted from Levy and Meltzer's model of the effect of health insurance on health outcomes, and known causal pathways linking asthma controller medication adherence to reductions in short-term complications.

In Aim 1, we will conduct in-depth qualitative interviews with approximately 60 commercially-insured patients with asthma or parents of children with asthma who have HDHPs with and without PDLs, or traditional plans. These telephone interviews will explore how patients and their families understand and navigate their HDHP and make health care decisions and trade-offs when faced with out-of-pocket costs. Insights gained from these interviews will shape and inform the quantitative analyses in Aims 2-4.

[figure not shown]
In Aims 2-4, we will maximize internal validity, reduce selection bias, and address causal inference standards by employing cutting-edge study designs and analytic methods that we have used in our prior work (CI-1,4): (1) ITS with comparison series design, the most rigorous quasi-experimental design for causal inference; (2) a population whose employers offer only a single health plan type, minimizing self-selection bias; (3) matching groups on the functional form of the baseline trend, recently shown to approximate estimates from RCTs; and (4) a rigorous and validated two-level propensity score matching approach that matches on both individual and employer baseline characteristics and includes family-level characteristics. We will follow individuals and families with asthma for 1 year before and up to 3 years after an index date when they are required to switch to HSA-HDHPs with or without PDLs, or to remain in HSA-HDHPs without PDLs or remain in traditional plans. We will identify two primary intervention groups of interest: 1) patients with asthma switched by employers from traditional plans to HSA-HDHPs *without* PDLs; and 2) patients switched from HSA-HDHPs *without* PDLs to HSA-HDHPs *with* PDLs. Patients in each group will be propensity-matched to patients with asthma who remain by employer choice in the same plan.

### **Conceptual Model Underlying Study Hypotheses**

The theoretical underpinnings of our study derive from Levy and Meltzer's conceptual model of the effect of health insurance on health outcomes, and known causal pathways linking asthma controller medication adherence to short-term complications. In our model (Figure 2), level of medication cost-sharing for patients with asthma is determined by plan type, as follows: 1) HSA-HDHPs without PDLs - full cost-sharing for controller and rescue medications; 2) HSA-HDHPs with PDLs - no cost-sharing for controller and rescue medications; and 3) traditional plans - three-tiered copayments for controller and rescue medications.

We hypothesize that higher cost-sharing in HSA-HDHPs without PDLs leads to decreased adherence to controller medications and decreased rescue medication use (offset by increased need for rescue medications due to suboptimal controller adherence). Reductions in controller medication use can increase asthma exacerbations and short-term complications such as ED visits and hospitalizations. Because a patient's OOP costs contribute to total family OOP cost burden, which can strain family budgets and lead patients to avoid or defer care and further decrease medication use, OOP costs are an additional outcome of interest. We hypothesize that lower cost-sharing due to PDLs, on the other hand, should lead to increased controller medication adherence, less need for rescue medications, fewer asthma complications, and lower OOP costs and family cost burden.

**Figure 2. Conceptual model** illustrating the impact of HSA-HDHPs with and without PDLs relative to traditional plans. Green arrows represent patterns of medication use, with wider arrows representing greater use.

### Sources of Data (IR-1)

The project's four-year duration will enable us to collect data from qualitative interviews on patient-reported experiences (Aim 1) that will inform quantitative analyses (Aims 2-4) and will allow us to accrue an adequate sample size of patients who experience the "intervention" of switching to an HSA-HDHP with or without a PDL and have one to two years of follow up.

**Aim 1.** We will collect patient-reported data through in-depth qualitative interviews with patients with asthma or parents of children with asthma who are enrolled in HDHPs (with and without PDLs) or traditional plans. Interviews will be conducted by phone using an interview guide with open-ended questions designed to take approximately 45 minutes. Interviews will be audiotaped and transcribed. There will be two sources of data:

- 1) Interviews of health plan members in non-group and employer-sponsored plans, including those identified from national employer accounts from Harvard Pilgrim Health Care (HPHC) which has a partnership with the large national health insurer whose data will be used in Aims 2-4. HPHC is a large non-profit health plan based in New England which partners with the national health plan to provide services to members living outside New England.
- 2) Interviews of subjects recruited through the AAFA, a national non-profit organization founded in 1979 to control and prevent asthma and allergic conditions through patient education, public awareness, and support for research (see Section F.1).

**Aims 2-4** will use 14 years (2004-2017) of enrollment and benefits data, insurance claims, standardized cost data, geocoded census data, and credit report SES variables from a large U.S. commercial health plan obtained through Optum. We will have detailed benefit information for ~80% of employer groups obtaining coverage from the health plan. For employers with missing deductible levels, we have developed an imputation algorithm that has 97.0% sensitivity and 96.2% specificity (MD-2). The health plan links insurance claims to de-identified credit report data, including novel indicators of individual-level SES (household income and net worth) and imputed information on ethnicity based on member surname (MD-2, see 'Methods to monitor and address missing data', below). Data from this insurer have been used in published health services research studies and the study team has experience examining a range of health care outcomes using these data. The research team's extensive experience using these data will enable us to efficiently create analytic cohorts and study variables, building upon previously developed methods. We will leverage existing health plan data from 2004-2014 that the study team has used in other projects, and add data through 2017 in December 2017 (see Optum letters).

### **Description of Comparators (RQ-5)**

This project will assess the impact of the "intervention" of being switched to an HSA-HDHP with a PDL, relative to a control group that was not switched and remained in an HSA-HDHP, and of being switched to an HSA-HDHP without a PDL relative to a control group that was not switched and remained in a traditional plan. Comparator groups include:

**HSA-HDHP with PDL:** enrollment in an HSA-qualified HDHP with a PDL that exempts asthma controller and rescue medications from the deductible, after being switched by an employer from an HSA-HDHP without PDL or from a traditional plan. There is limited data on the effectiveness of HSA-HDHPs with PDLs on asthma outcomes, despite an estimated prevalence of 19% among HSA-HDHP enrollees based on the national health plan to be studied. Other VBID programs have shown modest increases in adherence to chronic medications.

**HSA-HDHP without PDL:** enrollment in an HSA-qualified HDHP without a PDL, after being switched by an employer from a traditional plan. Those who enroll in HSA-HDHPs without PDLs and do not switch will also be used as a control group for those who switch from HSA-HDHPs without PDLs to HSA-HDHPs with PDLs. Evidence in adult populations suggest a reduction in adherence to asthma medications for those enrolling in HSA-HDHPs without PDLs. In 2015, the prevalence of HSA-HDHPs among covered workers was 15%.

**Traditional plan:** enrollment in a plan with no or a low (<\$500) deductible through an employer who offers only one plan. Fifty-four percent of covered workers have traditional plans, with a baseline proportion of days covered (PDC) for asthma medications of 46%.

### **Study Population (PC-2)** (See section D below for further detail)

The **Aim 1** study population will consist of adults with asthma and parents of children with asthma. Eligible participants will be those who are currently enrolled in employer-sponsored and non-group health insurance plans (high-deductible plans with and without a PDL, or traditional plans). Participants will be drawn from two different populations. First, we will recruit members of a health plan in order to ensure representation of patients through their membership in HSA-HDHPs with and without PDLs. Second, we will recruit additional patients with asthma and their caregivers through AAFA in order to ensure representation of patients who have other health insurance carriers.

The health plan population will be identified through enrollment and claims data from HPHC among non-group plans and large national employer accounts. HPHC offers HSA-HDHPs with the same standardized, federally mandated benefits as the national health plan used in Aims 2-4, as well as a PDL containing similar medications, including asthma controller and rescue medications. Eligible patients will include adults aged 18-64 with a diagnosis of asthma and/or a child with asthma. Using methods from our previous asthma studies, an asthma diagnosis will be defined as having at least one inpatient, ED, or outpatient claim in the prior year with a diagnosis of asthma based on the following International Classification of Diseases, 9th edition (ICD-9) codes (up through 2015): 493.XX and ICD-10 codes (2015 and after): J45.2x, J45.3x, J45.4x, J45.5x, J45.90x, J45.990, J45.991, J45.998. We will select patients who have been enrolled in an employer-sponsored or non-group market HSA-HDHP with or without a PDL, or a traditional plan without a high deductible, for the prior year. We will identify other family members with asthma sharing the same insurance plan. Among those eligible in each sub-group outlined in Table 1 below, we will randomly select up to 140 from each cell to send a recruitment mailing/email, for a total of up to 660 patients or parents invited to participate.

The AAFA population will be recruited through postings to AAFA's Asthma Online Community, Educational Support Group, email listserv, Facebook page, newsletters, flyers, and/or other communication channels. These posts will include a description of preliminary eligibility criteria (i.e. have a diagnosis of asthma or are parents of children with asthma who currently have an employer-sponsored or non-group commercial plan).

Both the HPHC recruitment mailing/email and AAFA recruitment messaging will invite potential participants to complete a pre-screening questionnaire to confirm eligibility, either by phone or online via REDCap, a secure web application for data capture. The questionnaire will assess insurance plan type, asthma diagnoses in the family, as well as other sociodemographic characteristics. The study team will schedule interviews with eligible participants, selecting participants to ensure diversity of socioeconomic status, race/ethnicity, geographic location and asthma severity. Interviews will be conducted to reach the target distribution of sub-groups outlined in Table 1 below with equal numbers of each sub-group coming from HPHC and AAFA, or until thematic saturation is reached. If the team is particularly interested in one category, we may oversample from that sub-category. The totals below are approximate. We will offer a gift card incentive of \$50 for completed interviews.

| Table 1: Targeted study sample for interviews      | Traditional plan | HDHP      |             | Total     |
|--|------------------|-----------|-------------|-----------|
|  |                  | With PDL  | Without PDL |           |
| Adult with asthma                                  | 6                | 6         | 6           | 18        |
| Parent of child with asthma                        | 6                | 6         | 6           | 18        |
| Adult with asthma who also has a child with asthma | 6                | 6         | 6           | 18        |
| Total                                       | 18        | 18 | 18   | 54 |

For **Aims 2-4**, the study population will be drawn from 14 years of data from a large U.S. commercial health plan with membership in all 50 states and annual enrollment of ~30 million members. The eligible population will consist of adults aged 18-64 years and children aged 4-17 years with asthma in a baseline year while insured in a traditional plan; all subjects must have continuous insurance coverage with pharmacy benefits for at least 24 consecutive months. Study subjects must have spent a year in a traditional health plan with no or low deductibles prior to the switch to an HSA-HDHP without a PDL, or have spent a year in an HSA-HDHP without a PDL before switching to an HSA-HDHP with PDL, and then remain enrolled for at least one-year post-switch. Control group members spend a year in a traditional plan or a HSA-HDHP without PDL then remain that plan for at least another 12 months. As study groups for secondary analyses, we will also identify enrollees switching from traditional plans to HSA-HDHPs with PDLs for comparison with those remaining in traditional plans. We will also identify enrollees with other plan types, not just HSA-HDHPs, which appear to have PDLs in that they have lower cost-sharing for asthma medications compared to other non-preventive medications. Based on preliminary findings from qualitative interviews as part of Aim 1 of the project, we have learned the cost of asthma medications is a problem not only for enrollees in HSA-HDHPs but in other types of HDHPs and in traditional plans with low deductibles as well, so we will also identify enrollees who are switched from having no PDL to having a PDL. Each of these groups will be matched with controls who start in the same type of plan and remain in that type of plan without gaining a PDL.

Thus, to be included in the study, all subjects will have at least 12 months in both the Pre and Post periods. We selected a follow-up period of up to three years because we hypothesized that patients in HSA-HDHPs with PDLs might experience benefits that take longer than one year to manifest. A primary purpose of the pre period is to ensure precise matching between groups on both the level and trend in key baseline characteristics (e.g., employer characteristics, demographics, utilization patterns, etc.). Our difference-in-difference analyses will include annual-to-annual comparisons (baseline to follow-up year 1, baseline to follow-up year 2, etc.). This will allow intuitive comparisons such as "relative to controls, adherence among HSA-HDHP members with PDLs increased by 4% in follow-up year 1 compared to baseline, but by follow-up year 2, adherence had increased by 11% compared to baseline." We have used this approach in a variety of studies and find that it translates well to clinical and policy audiences. For analyses of outcomes in the second and third year post-switch, we will only include study group patients and their matched controls who have had that length of follow up. We will compare and report differences in baseline characteristics for the subgroups of study cohort members that remain enrolled for each additional year.

We will exclude those over age 64 who are eligible for Medicare. We will identify members with asthma during a 12-24-month period prior to the index date using the same claims-based algorithm used to identify HPHC members with asthma for the Aim 1 interviews, with the inclusion of ICD-9 codes 493.XX to identify a diagnosis of asthma through October 2015. This broad definition will include patients with *intermittent asthma* as well as those with *persistent asthma*, for whom controller medications are recommended. Subgroup analyses will focus on the subset of patients who meet the HEDIS definition of persistent asthma ( $\geq 1$  ED or inpatient visit with asthma as the principal diagnosis,  $\geq 4$  outpatient visits with any asthma diagnosis, or  $\geq 4$  asthma drug dispensing events in the baseline year).

Eligible employers are those that offer only one plan type in a given benefit year: 1) traditional HMO/PPO/POS plans (deductibles  $<\$1000$ , copayments of  $<\$50$  for most services, tiered copayments for medicines); 2) HSA-HDHPs without PDLs; or 3) HSA-HDHPs with PDLs. We will select “full-replacement” employers that replace a traditional plan with an HSA-HDHP without PDL, or replace an HSA-HDHP without PDL with an HSA-HDHP with PDL, for all employees at a given point in time; matched comparison employers will include those that keep all employees in their prior plan. Including only full-replacement employers is a key strategy used in multiple previous studies to reduce member self-selection bias. The index dates for HSA-HDHP enrollees will be the dates of the employer-mandated plan switch. Matched controls will have contemporaneous enrollment in traditional plans also mandated by their employers; index dates will be assigned to be the same as matched intervention enrollees. We will also include matched controls who remain in HSA-HDHPs without PDLs. To reduce bias due to dropout, we will censor both HDHP and control patients together when either one drops out, and weight the remaining population to retain its baseline demographic and clinical profile. We estimate that there will be 621,481 adults and 310,741 children with asthma from 2004-2017 who will meet our inclusion criteria: 18,000 asthma patients in HSA-HDHPs without PDLs, 4,222 in HSA-HDHPs with PDLs, and 910,000 in traditional plans.

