### Generalizability and Limitations

This study has several limitations. We include in our sample only members offered no choice in health plan selection (exogenous insurance choice). By doing so, we limit generalizability but minimize individual-level selection bias, the major threat to internal validity. Employer selection is still possible, but we minimize this via the two-stage propensity score matching approach. Propensity score matching cannot control for selection on unobserved characteristics, but our planned approach of matching on the baseline trend of outcomes of interest approximates the estimates of randomized controlled trials. Dropout is a problem in longitudinal studies in insured populations. In our analyses, we will track and document drop out from disenrollment and changing plans, and will compare baseline pre-index characteristics of members who have one, two or three years of follow up. Furthermore, we will censor propensity-matched members of our study and comparison groups together if one drops out, and adjust analyses by weighting the members present during a given period of interest based on the baseline distributions of their demographic and health characteristics. If drop out in the third year of follow-up ends up being substantial in the proposed study population, we will limit the follow-up period to 2 years.

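### Requiring 12 months of enrolment after the index date leaves first-year exit outside every planned dropout safeguard, so differential exit could bias the estimates unseen

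*Combined protocol and SAP*

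**What the plan says.** All references are to the combined protocol and SAP, section C.

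**Entry.** Under Study Population, "all subjects must have continuous insurance coverage with pharmacy benefits for at least 24 consecutive months". Switched members spend a year in the old plan, "then remain enrolled for at least one-year post-switch"; controls spend a year in their plan, "then remain that plan for at least another 12 months". The section sums up that "all subjects will have at least 12 months in both the Pre and Post periods".

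**Contrasts.** The difference-in-differences comparisons are annual: "baseline to follow-up year 1, baseline to follow-up year 2, etc". Years 2 and 3 use only patients, with their matched controls, who have been followed that long.

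**Dropout.** Matched patients are censored together when one leaves, and the analysts will "weight the remaining population to retain its baseline demographic and clinical profile". Generalizability and Limitations repeats this, promises to record dropout, and says the team "will compare baseline pre-index characteristics of members who have one, two or three years of follow up".

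**Protection against selection.** The Overview of Study Protocol relies on "a population whose employers offer only a single health plan type, minimizing self-selection bias".

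**The concern.** Enrolment in months 1-12 happens after the exposure and may be affected by it. Choosing employers that offer a single plan type removes choice within the employer, but it does not stop a member from leaving, for example for a spouse's coverage. That example is reasoning, not a rate in the documents.

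The Limitations section treats individual-level selection as the chief threat to validity and gives up some generalizability to avoid it. If members who would have responded differently leave during the first year, and do so unequally by arm, the stayers' contrast need not describe everyone who was switched. Year 1 is the only contrast that contains the full cohort. Years 2 and 3 are subsets of it and inherit whatever selection it carries. A large sample does not reduce this kind of error.

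**Working it through.** **1. Can the planned safeguards reach months 1-12?**

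- Paired censoring: every included subject is complete through month 12, so no matched set can be censored in year 1.
- Weighting: it restores the profile of the included cohort, which already omits first-year leavers.
- Dropout comparison: the groups have one, two or three years of follow-up. None has less than one.
- Cohort counts: Study Population gives 18,000 + 4,222 + 910,000 = 932,222 (also 621,481 + 310,741) as patients meeting the inclusion criteria, so these are already net of first-year leavers. If retention were 95% or 80% (assumed), the 18,000 would come from 18,000/0.95 = 18,947 or 18,000/0.80 = 22,500 members at index. That would leave 947 to 4,500 switched members unseen.

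**2. When does this cause bias?** For each arm let d be the share leaving in months 1-12 and g the stayer-minus-leaver difference in mean outcome change. The mean in everyone at index is (1 - d) x stayers + d x leavers, so stayers exceed it by d x g. Subtracting the arms (1 = switched, 0 = control):

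bias = d1 x g1 - d0 x g0.

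The documents give neither d nor g. Everything below is assumed and in PDC points; the sign follows that of g.

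| Exit, switched / control | Gap g | Bias |
|---|---|---|
| equal | equal in both arms | 0 |
| 10% / 5% | 10 in both arms | 0.10x10 - 0.05x10 = 0.5 |
| 15% / 5% | 10 in both arms | 1.5 - 0.5 = 1.0 |
| 20% / 5% | 20 in both arms | 4.0 - 1.0 = 3.0 |
| 10% / any | 10, switched arm only | 1.0 |
| 20% / any | 20, switched arm only | 4.0 |

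**3. One worked case.** Suppose 25% of switched members and 20% of controls leave, and the extra 5 per 100 would have changed by 20 points more than the stayers' mean m, while other leavers resemble stayers.

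- Against those who would have stayed at the control rate: (75m + 5(m + 20))/80 = m + 1.25.
- Against everyone at index: (95m + 5(m + 20))/100 = m + 1.0.

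The shift is 1.0 to 1.25 points, depending on the reference population.

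**4. Benchmarks for traditional plan to HSA-HDHP without PDL.**

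- Table 3 gives a detectable PDC difference of 1.0%. Treating PDC as a 46% proportion with 18,000 against 72,000 and 80% power at 0.05 gives 1.03 points one-sided or 1.16 two-sided. No SD or sidedness is stated, so 1.0 is taken as given; nothing here depends on it.
- With the same gap in both arms, the extra exit that produces 1.0 point is 1.0/g: 20, 10 or 5 percentage points for gaps of 5, 10 or 20.
- The hypothesised decrease is 5-9%. Read as points, 1.25 is 1.25/9 = 14% to 1.25/5 = 25% of it. Read as relative to 46%, the decrease is 2.3 to 4.1 points (0.05x46, 0.09x46) and 1.25 is 30% to 54% of it. The plan does not say which reading applies.

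**The case against.** **The rule has the same length in both arms, and difference-in-differences removes fixed leaver-stayer differences.** This stands: with equal exit and equal gaps the bias is zero. A reader might infer that self-selection does re-enter and that the year-1 estimates are biased. The documents do not support that. They give no exit rate, and some exit will be ordinary job change.

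**Matching absorbs much of the problem.** Controls are matched on baseline expenditures, morbidity score, medications, visits, income and family-level measures within employer propensity quartiles. For exit explained by these, the stayers' comparison remains fair, so it would be wrong to say that exit by high-cost patients must bias every outcome. But matching is done among stayers and cannot use what happens after the switch, and the Limitations section concedes that unmeasured selection remains.

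**The mechanism does not fit the PDL contrast.** As defined in the Overview and Study Population, both arms start in HSA-HDHPs without PDLs and the switched arm gains free asthma drugs, so any incentive favours staying. This stands. (The Aim 2 analysis text describes these switchers as coming from traditional plans, a separate discrepancy to reconcile.) Nor can a PDC shift be set against the hypothesised 1-4% PDL effect, which is a change in number of fills.

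**Year 1 is not called the main analysis, and the promise to record dropout has no time limit.** Both are correct. It cannot be said that leavers will go uncounted, only that no described comparison or weight includes them.

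**A full year has a practical use.** Out-of-pocket cost and financial burden are annual outcomes, and deductibles are annual. This stands and shapes the fix.

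**Conclusion.** The gap in the plan is established from its text: entry depends on enrolment after exposure, and no described safeguard reaches months 1-12. The Limitations section does not acknowledge the restriction. Whether bias follows is conditional. It requires exit, or the leaver-stayer gap in outcome change, to differ by arm beyond what matching removes. The concern is strongest for the traditional-to-HSA-HDHP contrast.

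Size and direction cannot be computed from the documents. The 1.0 to 1.25 points rests on two assumptions, 5 points of extra exit and a 20-point gap. A shift of that size would match or exceed the stated detectable difference but would not by itself account for the hypothesised decrease. The point is a worthwhile, inexpensive improvement, not a demonstration that the design fails.

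**What to change.** 1. Define the reference cohort as members with 12 months of baseline who are enrolled on the index date, and build the match on it.
2. Report first-year exit, and the baseline characteristics of leavers, by arm. This table alone would show whether exit differed between the arms.
3. Extend the planned weights back to this cohort, using the inverse probability of remaining enrolled through month 12.
4. Run the planned monthly series with members censored at exit.
5. Report the 12-month completer analysis alongside. For annual out-of-pocket outcomes keep full-year members, weighted to the index cohort.
6. State how the restriction of years 2-3 to those with that length of follow-up combines with censoring and weighting.

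The data are already held, so the cost is programming and slightly wider intervals. Two limits should be stated: the weights correct only for measured predictors of exit, and members who leave on hearing of the switch, before the index date, are still not covered.

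### Year-1, year-2 and year-3 effects come from different, shrinking cohorts, so an apparent change in effect across years could be inflated or masked by cohort change; same-cohort contrasts should be added

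*Combined protocol and SAP*

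**What the plan says.** All places are in the Combined protocol and SAP, section C (Approach).

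- **Cohorts.** Study Population (PC-2) states that "all subjects will have at least 12 months in both the Pre and Post periods", so the year-1 contrast uses the whole cohort. For years 2 and 3, "we will only include study group patients and their matched controls who have had that length of follow up". The cohorts are therefore nested and shrinking.
- **Reading across years.** The same section justifies up to three years of follow-up by the possibility that PDL benefits need more than a year to appear. It compares each follow-up year with baseline and offers, as a sample sentence for clinical and policy readers, that adherence "increased by 4% in follow-up year 1 compared to baseline, but by follow-up year 2, adherence had increased by 11% compared to baseline".
- **Safeguards.** Matched members are censored together, and the plan is to "weight the remaining population to retain its baseline demographic and clinical profile". Generalizability and Limitations repeats both measures. Baseline characteristics will be compared by length of follow-up, and follow-up may be cut to two years if third-year dropout is substantial; no threshold is given.
- **Data window.** Sources of Data (IR-1) covers 2004 to 2017 and says the team will "add data through 2017 in December 2017". It also expects one to two years of follow-up for switchers.

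I found no re-estimate of the year-1 effect in the members who reach year 2 or 3, no full list of weighting variables, and no retention rate.

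**The concern.** A year-2 estimate can differ from a year-1 estimate because the effect in individuals changed, or because the people averaged over changed. The plan sets the two side by side without separating these sources. Two mechanisms change the people: disenrolment or plan change, and the end of the data, which removes late switchers whatever their behaviour.

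The time course matters here. Delayed benefit is the stated reason for the length of follow-up, and the section on barriers to dissemination expects the research to show learning effects. An employer or insurer told that the benefit builds up might act on a pattern that partly reflects who stayed. Equally, a real build-up could be hidden.

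**Working it through.** The plan states no figure on this point, so there is none to reproduce. Retention and effect gaps below are assumptions; the rules on cohorts, weights and data window are from the sections cited above.

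**1. Calendar limit.** If claims are complete to 31 December 2017, 24 months of follow-up require a switch by about 1 January 2016, and 36 months a switch by about 1 January 2015. Later switchers, up to about 1 January 2017, can contribute to year 1 but not to the later year or years.

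**2. Cohort change with constant individual effects, before weighting.** Let s be the share of the year-1 cohort that is also in the year-2 cohort, S the effect in those members and L the effect in the others, both constant over time.

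- Year 1 = s × S + (1 − s) × L
- Year 2 = S
- Apparent change = (1 − s) × (S − L)

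With assumed S = 5 and L = 2 PDC points:

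| s | Year 1 | Year 2 | Apparent change |
|---|---|---|---|
| 80% | 0.8×5 + 0.2×2 = 4.4 | 5.0 | +0.6 |
| 60% | 0.6×5 + 0.4×2 = 3.8 | 5.0 | +1.2 |
| 40% | 0.4×5 + 0.6×2 = 3.2 | 5.0 | +1.8 |

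With the effects exchanged (S = 2, L = 5) the apparent changes are −0.6, −1.2 and −1.8. For scale only, Table 3 prints 2.0 points as the least detectable overall PDC difference for the PDL contrast.

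**3. What weighting removes.** Assume a two-level modifier, half the cohort at each level, with constant effects of 8 and 0 (mean 4) and retention of 75% and 45% per year (mean 60%).

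- Share of the high-effect level in year 2: 0.75 / (0.75 + 0.45) = 0.625, so the mean effect is 8 × 0.625 = 5.0.
- Share in year 3: 0.5625 / (0.5625 + 0.2025) = 0.735, so the mean effect is 8 × 0.735 = 5.9.
- Modifier in the weights: the shares return to one half and the course is 4.0, 4.0, 4.0.
- Modifier unmeasured: the course stays 4.0, 5.0, 5.9.

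A simulation with 400,000 members gave the same values.

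**4. Limit on what cohort change alone can do.** To turn 4 into 11 with constant effects, L = (4 − 11s) / (1 − s). This is −24 points at 80% retention, −6.5 at 60% and −3.0 at 50%.

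**5. Same-cohort contrast.** If both years are estimated in the members who reach year 2, with the same weights, constant effects give S − S = 0. The cohort-change term is zero by construction.

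**The case against.** The case on the other side has force.

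- **There is no planned conclusion of growth.** A reader might infer from the 4% and 11% sentence that a build-up is to be concluded. The sentence is a hypothetical reporting example, the delayed benefit is put as a possibility, and the hypotheses for Aims 2 to 4 do not mention growth. That reading is not supported. The intention to present the years side by side remains.
- **The safeguards are aimed at this problem.** Step 3 shows that weighting removes the artefact for modifiers in the weights. It does not for unmeasured ones. Generalizability and Limitations itself says that patient attitudes and provider factors affect adherence but are not measured, and that HSA balances, which may affect use, are not available for all members.
- **Calendar trends are partly handled.** Controls are contemporaneous and share the index date, so each contrast removes trends common to both groups. What is left is an effect that itself differs by switch year. The weighting variables are not fully listed, so the absence of switch year is a gap in the text and not a proven omission.
- **Adherence is also modelled monthly.** The Analysis plan fits interrupted time series with level and trend terms. Because everyone has 12 months after the switch, the first-year trend comes from a fixed cohort. This does not extend to years 2 and 3.
- **The illustration is unweighted and assumed.** That stands. Nor should it be set against the 1-4% in Hypothesized Effect Size, which refers to number of fills and not to PDC points.

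**Conclusion.** The point holds as a limit on comparison across years. As planned, a rise or fall from year 1 to year 2 or 3 mixes change over time with change of cohort, and the safeguards remove only the part explained by variables in the weights.

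The size cannot be fixed from the documents. Before weighting, an assumed 3-point gap between stayers and leavers gives 0.6 to 1.8 PDC points at 80% to 40% retention, in either direction. After weighting, only the part due to unmeasured or unweighted modifiers remains.

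Two stronger readings are not supported. One is that the yearly estimates are invalid: each has its own baseline year and matched controls, and nothing here shows a fault in any single year. The other is that a step from 4% to 11% could come from cohort change alone: step 4 shows that this would need low retention and sharply different effects.

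**What to change.** Keep the planned weighted full-cohort estimates for each year, and add to them:

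- the year-1 effect re-estimated in the year-2 cohort;
- the year-1 and year-2 effects re-estimated in the year-3 cohort, in each case with the same patients, baseline year and weights;
- a list of the weighting variables, including index year. This can rebalance only index years represented in the later cohort. It cannot restore switchers too late to reach that year, so the same-cohort contrast is still needed;
- a reporting rule: claim growth or delay of effect only when the same-cohort contrasts support it, and state that those contrasts apply to members with longer enrolment.

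The cost is a few extra runs of models already planned and some added text, with no new data. The added contrasts are less precise and describe longer-enrolled members only, which is why they belong beside the full-cohort results and do not replace them.
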